#### **14.4 Study Population**

Twenty-four eligible patients with p16INK4a negative/HPV-unrelated OPSCC, larynx SCC, hypopharynx SCC, and oral cavity SCC will be enrolled into the trial to receive 2 months of neoadjuvant palbociclib monotherapy at Step One, 6-7 weeks CRT (either cisplatin or cetuximab) at Step Two, and 6 months of adjuvant palbociclib at Step Three. The sampling method is non-random. Patients with excellent performance status and adequate vital organ function at enrollment will be assigned to the cisplatin cohort. Patients with reduced performance status and/or vital organ function will be assigned to the cetuximab cohort.

#### **14.5 Power Analysis and Sample Size**

Power analysis is conducted based upon the primary endpoint. The results of a small phase I trial of palbociclib and cetuximab in RM-HNSCC (Michel, et al., 2016) showed a tumor response rate of 22% (2 of 9 pts). In the phase I trial, the tumor response rate was 17% (1 of 6 pts) in cetuximab-resistant disease, supporting an independent effect of palbociclib in this disease. Assuming the true tumor response rate with palbociclib monotherapy in patients with p16INK4a negative untreated HNSCC could be substantially higher than 17%, a sample size of 24 patients yields a >80% power if the true tumor response rate is at least 38%, using a one-sided exact test at the significance level of 0.05 and null response rate of 17%. PASS 15.0 was used for sample size calculation. The results of this exploratory study are considered hypothesis-generating, and will provide critical baseline information to develop future confirmatory trials.

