#### **14.6 Data Analysis**

All data will be evaluated as observed, and no imputation method for missing values will be used. All data will be presented in a descriptive manner. All analyses are considered as exploratory, even if statistical tests are used.

Descriptive statistics will be used to summarize the trial results, i.e., statistics for continuous variables may include means, medians, ranges and appropriate measures of variability. Qualitative variables will be summarized by counts and percentages. The uncertainty of estimates will be assessed by confidence intervals.

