##### **14.6.1 Primary Endpoint Analyses**

The tumor response rate to neoadjuvant palbociclib monotherapy at the end of step one and the corresponding 95% confidence interval will be calculated for the whole sample. Exact binomial one sample proportion test will be conducted to compare the estimated tumor response rate to a null response rate of 17%.

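### Section 14.5 claims more than 80% power at a 38% response rate with 24 patients; the one-sided exact test it names has 74.9%.

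*Combined protocol and SAP*

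**What the plan says.** Section 14.5 bases the sample size on the primary endpoint, the response rate (CR or PR) at the end of step one. It states that "a sample size of 24 patients yields a >80% power if the true tumor response rate is at least 38"%. The test behind this figure is one-sided and exact, with a level of 0.05 and a null rate of 17%. The software is named ("PASS 15.0 was used for sample size calculation"), but neither a critical value nor an attained significance level is given.

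Section 14.6.1 plans the same test for the analysis: "Exact binomial one sample proportion test will be conducted to compare the estimated tumor response rate to a null response rate of 17"%. It adds that "the corresponding 95% confidence interval will be calculated for the whole sample", without naming the interval method or repeating that the test is one-sided at 0.05. Section 14.4 plans 24 eligible patients and makes no allowance for attrition. Section 14.6 states: "All analyses are considered as exploratory, even if statistical tests are used".

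**The concern.** Section 14.5 supplies every input needed to compute the power: the sample size, the test, its direction and level, the null rate and the alternative. The test named for the design is also the one planned for the analysis, so the stated power should be the power of that test. An exact binomial test on 24 patients can attain only a few significance levels. A figure so close to 80% may therefore have come from a continuous approximation that ignores this.

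This power statement is the only quantitative support for enrolling 24 patients. A reader who trusts it would take a non-significant result, say 7 of 24, as having had less than a 20% chance of arising if the true rate were 38%. Section 14.5 also says the results will inform later confirmatory trials, and a design reused with the same calculation would carry the error forward.

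**Working it through.** **Inputs, all from section 14.5:** n = 24; null rate p0 = 0.17; alternative p1 = 0.38; one-sided alpha = 0.05; exact binomial test. X is the number of responders.

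**Trying to reproduce the stated figure.** The usual normal approximation, with the null variance for the critical value, the alternative variance for the power and no continuity correction, is

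power = Φ{ [ (p1 − p0)√n − 1.645·√(p0(1 − p0)) ] / √(p1(1 − p1)) }

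- (0.38 − 0.17)·√24 = 1.0288
- √(0.17 × 0.83) = 0.3756, times 1.645 = 0.6179
- √(0.38 × 0.62) = 0.4854
- Φ[(1.0288 − 0.6179)/0.4854] = Φ(0.8466) = 80.1%

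This matches the claim, but it is not the exact test. It places the rejection boundary at 0.17 + 1.645 × 0.3756/√24 = 0.296, or 7.1 responders, and treats the count as continuous. A real count must reach 8. Whether the stated figure arose this way is an inference, because the plan does not show the software settings.

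**The exact test.** The critical value is the smallest r with P(X ≥ r | 24, 0.17) ≤ 0.05. Power is P(X ≥ r | 24, 0.38).

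| Reject at | Type I error at 17% | Power at 38% |
|---|---|---|
| ≥ 7 | 0.0992 (not allowed) | 0.8658 |
| ≥ 8 | 0.0394 | **0.7487** |
| ≥ 9 | 0.0134 | 0.5963 |

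The rule is therefore 8 or more of 24. Power is 74.9%, and the type II error is 1 − 0.7487 = 25.1%.

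**Can another reading rescue the figure?**

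- Rounding of the null: 1/6 (the phase I source of the 17%), 16.5% and 17.49% all keep the cut-off at 8, so power stays at 74.9%.
- Rounding of the alternative: 38.49% gives 76.4%.
- A randomised exact test that spends the whole 0.05 gives 77.0%.
- The continuity-corrected normal approximation gives 73.8%, and the arcsine approximation 75.8%.
- Alpha of 0.10 gives 86.6% (cut-off 7), but contradicts the stated 0.05.

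**What 24 patients do deliver.** With the cut-off at 8, power is 80.8% at a true rate of 40% and reaches 80% at about 39.7%.

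**What the stated claim would need.** The exact test at p1 = 0.38, by sample size:

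| n | Reject at | Alpha | Power |
|---|---|---|---|
| 24 | 8 | 0.0394 | 0.7487 |
| 25 | 8 | 0.0495 | 0.7932 |
| 26 | 9 | 0.0232 | 0.7070 |
| 27 | 9 | 0.0297 | 0.7543 |
| 28 | 9 | 0.0373 | 0.7960 |
| 29 | 9 | 0.0462 | **0.8322** |
| 30 | 10 | 0.0224 | 0.7599 |
| 31 | 10 | 0.0282 | 0.7991 |
| 32 | 10 | 0.0349 | 0.8334 |

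The smallest adequate size is 29. Power dips below 80% again at 30 and 31, and stays above it from 32 to 44, the largest size checked.

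**Attrition.** Section 5.4 lets some patients be non-evaluable for response, and section 14.6 rules out imputation. If such patients leave the denominator, the cut-off stays at 8 and power falls to 69.8% with 23 evaluable patients and 64.1% with 22.

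**The case against.** The strongest reply is that little depends on the figure. The study is described as exploratory and hypothesis-generating. The exact test protects the type I error whatever power was claimed. The null rests on 1 response in 6 patients, and the alternative is loosely motivated. Against that uncertainty, moving the rate detectable with 80% power from 38% to about 39.7% is a small shift.

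All of that is true, and it limits the seriousness of the point. It does not make the number right: the exploratory label governs how results are interpreted, not whether a stated power matches its stated test. The type II error at 38% is 25.1%, where the text implies under 20%.

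A second reply is that the confidence interval in section 14.6.1 is a separate matter, and that a two-sided 95% interval need not agree with a one-sided 5% test. That is also fair. At 8 of 24 the one-sided exact p-value is 0.039, while the Clopper-Pearson 95% interval (15.6% to 55.3%) still contains 17%. Nothing in the plan judges success by the interval, so this calls for clearer reporting and is not a fault in the decision rule.

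**Conclusion.** The power statement in section 14.5 is wrong for the test it names. Exact power at 38% is 74.9%, about 5 percentage points below the claim, and 80% is reached only at a true rate of about 39.7%. The result uses only inputs printed in section 14.5 and assumes that all 24 patients contribute to the analysis; losses would lower it further. Rounding of the inputs does not change the conclusion. The primary analysis remains valid, with an attained one-sided alpha of 0.039. The error should be corrected, but it does not undermine the trial.

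**What to change.** Restate section 14.5 along these lines: 24 patients; the null is rejected with 8 or more responses; exact one-sided alpha 0.039; power 75% at a true response rate of 38% and 81% at 40%. The sample size need not change for an exploratory trial. If the team prefers to keep more than 80% power at 38% with the exact test, the minimum is 29 patients, or 32 or more to stay clear of the dip at 30 and 31, before any allowance for non-evaluable patients.

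As a minor clarification, section 14.6.1 could repeat that the test is one-sided at 0.05 and name the interval method. The repetition is useful because a two-sided exact p-value at 8 of 24 is 0.051. If Clopper-Pearson is chosen, a 90% interval reported beside the test agrees with it (17.8% to 52.1% at 8 of 24), and the 95% interval can stay as description.

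The cost is a reworded sentence in 14.5 and a phrase in 14.6.1, with no extra patients and no change of test. The stated power becomes less favourable.

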#### **14.6 Data Analysis**

All data will be evaluated as observed, and no imputation method for missing values will be used. All data will be presented in a descriptive manner. All analyses are considered as exploratory, even if statistical tests are used.

Descriptive statistics will be used to summarize the trial results, i.e., statistics for continuous variables may include means, medians, ranges and appropriate measures of variability. Qualitative variables will be summarized by counts and percentages. The uncertainty of estimates will be assessed by confidence intervals.

##### **14.6.1 Primary Endpoint Analyses**

The tumor response rate to neoadjuvant palbociclib monotherapy at the end of step one and the corresponding 95% confidence interval will be calculated for the whole sample. Exact binomial one sample proportion test will be conducted to compare the estimated tumor response rate to a null response rate of 17%.

##### **14.6.2 Secondary Endpoints Analyses**

Local-regional disease relapse rate and distant metastases rate and their corresponding 95% confidence intervals will be calculated in each cohort, separately. PFS and OS at two-year will be presented in subject listings. PFS and OS will be analyzed by Kaplan-Meier method in each cohort, separately. Paired t-test or paired-sample Wilcoxon Signed Rank test will be used to compare the genomic, RNA, and protein expression data derived at baseline and then after two cycles of neoadjuvant palbociclib monotherapy. The association between the genomic, RNA, and protein expression data derived after 2 cycles of palbociclib monotherapy and local-regional disease relapse/distant metastases will be explored through independent t-test, Fisher's Exact test, or Kruskal-Wallis test as appropriate.

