### 1.3 Biology of p16INK4a negative (HPV-unrelated) HNSCC

HNSCC is a heterogeneous disease. Based on unique gene expression signatures, at least four subgroups have been defined, each with distinct signaling pathways. Despite this heterogeneity, aberrant cell cycle regulation is a ubiquitous event. The mechanism underlying unrestrained proliferation varies depending on the tumor's transcriptionally-active HPV status. In HPV-related HNSCC, E7 viral protein drives unrestrained proliferation by promoting Rb degradation. In HPV-unrelated HNSCC, Rb inactivation occurs through hyper-activation of the Rb inhibitory complex CDK4/cyclin D. CCND1 (encoding cyclin D1, the regulatory subunit of the complex) is amplified and/or the CDK4/6 inhibitor p16INK4a is inactivated in nearly all of these cancers. Alterations of CCND1 and p16INK4a are rare in HPV-related HNSCC. As a result, p16INK4a is overexpressed in HPV-related HNSCC and under expressed in HPV-unrelated HNSCC.

The genetics of HPV-unrelated HNSCC influences the clinical course. CCND1 amplification and p16INK4a inactivation are poor prognostic factors in HNSCC, in part because cyclin D1 overexpression adversely affects tumor response to EGFR inhibitors and cisplatin. In HNSCC cell lines, cyclin D1 amplification and/or overexpression

correlated with resistance to these drugs. Studies in HNSCC reveal that cyclin D1 overexpression is predictive of resistance to cisplatin.

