## **2.3 Exploratory Objectives**

1. Explore potential pharmacodynamic determinants of tumor response to palbociclib monotherapy using genomic, RNA, and protein expression methods.
2. Explore potential pharmacodynamic determinants of locoregional disease relapse risk and distant metastases risk to palbociclib-based therapy using genomic, RNA, and protein expression methods.

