## **9.0 CORRELATIVE STUDIES**

### **9.1 Tumor Biopsy**

Tumor biopsies (core or excisional/incisional) will be used to perform whole exome sequencing (WES), RNAseq, p16INK4a expression, Ki-67 by IHC, total and phospho-Rb by IHC, Cyclin D1 by IHC, Cyclin E by IHC, Cyclin A by IHC, p53 by IHC, p21 by IHC, p27 by IHC, and TUNEL assay. Reverse phase protein array (RPPA) will be performed. RPPA is a high-throughput antibody-based technique developed for Functional Proteomics studies to evaluate protein activities in signaling networks. Additional analyses of other potential biomarkers may be performed as they emerge from the scientific understanding of palbociclib activity. If a biopsy is not feasible for financial reasons or safety concerns, at the Primary Investigator's discretion, the biopsy may be foregone.

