#### **9.1.1 Collection of Specimens**

Tumor tissue will be collected at baseline and then after two cycles of neoadjuvant palbociclib monotherapy (conclusion of Step One). It should be collected from the primary tumor site if possible, but involved neck nodal tumor tissue is an alternative. If possible, the same site should be biopsied at baseline and end of C2.

The biopsy should consist of a minimum of 4 needle cores (14-18 gauge is preferred) if neck nodal tissue or 2 small (each 4 x 4 x4 mm) pieces of tumor if primary tumor site tissue.

If the patient has been previously enrolled in Washington University's TAP protocol (head and neck bank, HRPO #201102323), tissue that has been banked may be accessed in lieu of fresh biopsy at baseline.

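### Relapse is related only to marker levels after palbociclib, so a marker already prognostic at baseline can be mistaken for a pharmacodynamic determinant

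*Combined protocol and SAP*

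**What the plan says.** Exploratory objective 2 in Section 2.3 reads: "Explore potential pharmacodynamic determinants of locoregional disease relapse risk and distant metastases risk to palbociclib-based therapy using genomic, RNA, and protein expression methods". Section 14.6.2 provides two separate marker analyses:

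- **Before and after, without outcome:** "Paired t-test or paired-sample Wilcoxon Signed Rank test will be used to compare the genomic, RNA, and protein expression data derived at baseline" and after two cycles.
- **Outcome, without baseline:** "The association between the genomic, RNA, and protein expression data derived after 2 cycles of palbociclib monotherapy and local-regional disease relapse/distant metastases", explored by "independent t-test, Fisher's Exact test, or Kruskal-Wallis test as appropriate".

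The baseline material is planned. Section 9.1.1 states: "Tumor tissue will be collected at baseline and then after two cycles of neoadjuvant palbociclib monotherapy". Section 5.0 does mention pre- and post-treatment tissue together, but for determinants of tumor response, not of relapse. No section relates relapse to the baseline level, to the change from baseline, or to the post-treatment level adjusted for baseline.

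Section 1.3 says that CCND1 amplification and p16INK4a "inactivation are poor prognostic factors in HNSCC". The assay list in Section 9.1 includes "Cyclin D1 by IHC" and p16INK4a expression.

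**The concern.** A pharmacodynamic determinant of relapse is naturally read as something the drug did to the tumor that bears on later relapse. The level after two cycles is not that quantity. It contains what the tumor was like beforehand as well as any drug effect. If relapsers already differed at baseline, the post-treatment level can differ even when palbociclib moved the marker equally in both groups.

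The protocol makes this plausible for at least part of the panel, because it calls two pathway alterations prognostic and measures related proteins. The trial has no untreated arm, so each patient's own baseline biopsy is the only internal reference, and this analysis leaves it out.

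Two errors are possible. A prognostic marker may be read as a drug-effect marker. A real difference in drug effect between relapsers and non-relapsers may be lost in the spread of baseline levels. Section 14.5 says the results are meant to inform later confirmatory trials, so either error could affect what is studied next.

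**Working it through.** The plan gives no power or error rate for the marker analyses, so there is no stated figure to reproduce. It also gives no marker SD, baseline difference or pre/post correlation. All inputs below are therefore assumptions.

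**Inputs.** 20 pairs, 10 relapse and 10 no relapse. Section 1.2 cites local-regional failure of 52% in p16-negative oropharynx and 20% in larynx, so an even split is only one possibility. Baseline difference d of 0.3 to 1.0 within-group SD. Correlation r of 0.5 or 0.7. Two-sided 5% tests, log scale.

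**Two models without a pharmacodynamic link to relapse**

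- *Model A (regression to the mean):* post = −0.5 + r × baseline + √(1 − r²) × noise. The post-treatment groups differ by r × d.
- *Model B (stable tumor level, independent biopsy noise, equal shift of −0.5 in everyone):* the post-treatment groups differ by d.

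**Post-only t-test.** With 10 per group the noncentrality is difference ÷ √(1/10 + 1/10) = difference × √5 = 2.236 × difference, on 18 df. For d = 0.8 and r = 0.7:

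- Model A: 2.236 × 0.7 × 0.8 = 1.25, rejection 22.0%.
- Model B: 2.236 × 0.8 = 1.79, rejection 39.5%.

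**Change.** Its SD is √(2(1 − r)).

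- Model A: the groups differ in mean change by (1 − r)d in size, so the noncentrality is 2.236 × d × √((1 − r)/2).
- Model B: the mean change is equal, so rejection is 5%.

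**Baseline-adjusted post level.**

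- Model A: this regression is the generating model, so 5% is built in.
- Model B: the slope on a noisy baseline is r rather than 1, which leaves an expected difference of (1 − r)d. Rates were simulated with 40,000 data sets per setting.

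| d (SD) | r | A: post-only | A: change | A: adjusted | B: post-only | B: change | B: adjusted |
|---|---|---|---|---|---|---|---|
| 0.3 | 0.5 | 6.2% | 6.2% | 5% | 9.7% | 5% | 6.3% |
| 0.3 | 0.7 | 7.3% | 5.7% | 5% | 9.7% | 5% | 5.8% |
| 0.8 | 0.5 | 13.5% | 13.5% | 5% | 39.5% | 5% | 14.1% |
| 0.8 | 0.7 | 22.0% | 10.1% | 5% | 39.5% | 5% | 10.0% |
| 1.0 | 0.5 | 18.5% | 18.5% | 5% | 56.2% | 5% | 18.7% |
| 1.0 | 0.7 | 31.7% | 13.0% | 5% | 56.2% | 5% | 12.4% |

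Neither alternative holds 5% in both models. Change fails somewhat in Model A, and at r = 0.5 it does no better there than the post-only test. Adjustment fails somewhat in Model B. Each is sound where the other is weak, which is the reason to show both.

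**Number of pairs.** In Model B at 0.8 SD with half relapsing, the post-only rate is about 46% with all 24 patients paired and about 32% with 16 pairs.

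**Scale.** If the drug suppresses a marker proportionally, raw change still tracks baseline. In simulations of 24 patients with 50% relapse (differences 0.5 to 1.2 SD, correlations 0.5 to 0.9), raw change rejected in 7% to 45%, against about 5% on the log scale.

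**Masking.** Take no baseline difference and a true differential drug effect of 0.8 SD, again 10 v 10. Post-only power is about 39%. Baseline-adjusted power is about 47%, 63% and 96% at r = 0.5, 0.7 and 0.9.

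**The case against.** The strongest reply is that the plan claims little. Section 14.6 labels every analysis exploratory, Section 14.5 calls the results hypothesis-generating, and Section 2.3 speaks only of potential determinants. The protocol never defines a pharmacodynamic determinant as a change score, and residual marker level after drug exposure is a legitimate exploratory predictor of relapse. The paired analysis also examines what the drug does to each marker, though without outcome. This stands as a reason to keep the post-level comparison and to rate the point as minor. It does not supply the missing link, because neither planned analysis connects what changed with who relapsed.

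Four further limits stand:

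- Section 1.3 names two tumor alterations and gives no effect size. It does not show that Ki-67, phospho-Rb or the RNA and protein array markers are prognostic at baseline.
- Change has little meaning for largely fixed genomic calls.
- A baseline difference of 0.8 SD is large. At 0.3 SD the post-only rate is only about 6% to 10%.
- Pairs may be fewer than 24 and noisier than assumed. Section 9.1 lets a biopsy be omitted, and Section 9.1.1 asks for the same site only where possible and accepts banked baseline tissue.

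A reader might infer that prognostic markers will be reported as drug-effect markers, or that adjusting for baseline cures the problem. The documents do not support the first, since nothing commits the trial to that label or to carrying a marker forward on this test. The table does not support the second.

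**Conclusion.** The point holds as a limitation of one exploratory objective. Followed as written, Section 14.6.2 cannot separate a marker that was prognostic before treatment from one whose response to palbociclib bears on relapse. Misattribution can occur; it is not certain, and it concerns only markers whose baseline level is prognostic.

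Under the assumed inputs the planned test flags such a marker in about 6% to 56% of data sets. Log-scale change or baseline adjustment flags about 5% to 14%, except at r = 0.5 with a 1.0 SD difference, where each reaches about 19% in its unfavorable model. These figures illustrate the mechanism and do not predict this trial's results. The primary endpoint and the other secondary analyses are untouched. In a single-arm trial, with chemoradiation and adjuvant palbociclib given after the second biopsy, no version of the analysis can show that palbociclib caused the link.

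**What to change.** In Section 14.6.2, for continuous expression markers:

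1. Add the association of local-regional relapse and of distant metastases with the paired change from baseline, on the log scale where suitable, and name it as the pharmacodynamic analysis for exploratory objective 2.
2. Add, as a sensitivity analysis, a regression of the post-treatment level on relapse status and baseline level. Treat a marker seen in only one of the two with caution.
3. Report the association of the baseline level with relapse beside these, labeled prognostic.
4. Keep the planned post-level comparison as descriptive.
5. Report the number of pairs used, and state that the single-arm design cannot attribute any link to palbociclib.

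Largely fixed genomic calls need no change score; relate their baseline status to relapse as prognostic.

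The cost is analysis wording only. Both biopsies are already planned, and no visits, samples or patients are added. The downside is that patients without paired biopsies drop out of this exploratory analysis. The added tests also increase the number of comparisons, which is why one should be named in advance as the lead.
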